8.5 STUDY HALTING RULES

The study may be halted at any time by the sponsor, the IRB, Health Canada or the FDA due to safety concerns. Examples of findings that might trigger a safety review are the number of SAEs overall, the number of occurrences of a particular type of SAE, severe AEs/reactions, or increased frequency of events. If the study is halted, the sponsor will immediately notify all investigational sites, the IRB(s) and the applicable regulatory authority.

8.6 SAFETY OVERSIGHT

Independent oversight is an important component to ensure human subjects' protection. Safety oversight will be under the direction of the sponsor and a medical monitor.

9 CLINICAL MONITORING

Clinical site monitoring is conducted to ensure that the rights and well-being of human subjects are protected, that the reported trial data are accurate, complete, and verifiable, and that the conduct of

the trial is in compliance with the currently approved protocol/amendment(s), with GCP, and with applicable regulatory requirement(s).

- Monitoring for this study will be performed by the sponsor or designate.
- On-site monitoring will occur within 4 weeks of first enrolled subject and will occur at a frequency described in the Monitoring Plan.
- Variables to be monitored will be described in the Monitoring Plan.
- The Study Director or designate will be provided copies of monitoring reports within 15 business days of visit.
- The sub-investigator will provide on-site monitoring weekly during the study period to ensure patient safety and verify accurate data collection.
- The clinical site will perform internal quality management of study conduct, data collection, documentation and completion. An individualized quality management plan will be developed to describe a site's quality management.

10 STATISTICAL CONSIDERATIONS

10.1 STATISTICAL AND ANALYTICAL PLANS

An initial statistical analysis plan has been developed and will be finalized once all data collection is complete.

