4.2.1 PRIMARY ENDPOINT

As skin ages, collagen can become disorganized, causing changes in both the mechanical property of the skin and skin appearance. The change in gross elasticity ($R2$ or Ua/Uf which is a ratio of maximum recovery (Ua) and skin distensibility (Uf)) as measured by a Cutometer® has been found to be one of the most suitable parameters to represent the influence of aging on skin mechanical properties.¹ This is expressed as a percentage, the closer the value is to 1 (100%), the more elastic the skin. Thus, the primary endpoint will be the change in gross elasticity after treatment with combined RF and PEMF. The gross elasticity of facial skin will be measured prior to the start of the treatment regimen (baseline), and 20 weeks after completion of the treatment regimen.

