Subjects will be discharged from the clinic and will be instructed to return for the Visit 6, Week 5 assessment and treatment.

Visit 6, Week 5

Subjects will return to the clinic one week (± 3 days) after the last treatment. Adverse events and any changes to concomitant medications will be recorded.

Subjects will receive treatment of the face as described above in section 7.3.2. Following treatment, the investigator will examine the treated area and report immediate response.

The assessment of discomfort/pain will be based on the subject's completion of the 100 mm VAS immediately after treatment.

Subjects will be discharged from the clinic and will be instructed to return for the Visit 7, Week 6 assessment and treatment.

Visit 7, Week 6

Subjects will return to the clinic one week (± 3 days) after the last treatment. Adverse events and any changes to concomitant medications will be recorded.

Subjects will receive treatment of the face as described above in section 7.3.2. Following treatment, the investigator will examine the treated area and report immediate response.

The assessment of discomfort/pain will be based on the subject's completion of the 100 mm VAS immediately after treatment.

Subjects will be discharged from the clinic and will be instructed to return for the Visit 8, Week 7 assessment and treatment.

Visit 8, Week 7

Subjects will return to the clinic one week (± 3 days) after the last treatment. Adverse events and any changes to concomitant medications will be recorded. Photographs will be taken as described above in section 7.3.2. Cutometer® measurements of the treated area will be obtained.

Subjects will receive treatment of the face as described above in section 7.3.2. Following treatment, the investigator will examine the treated area and report immediate response.

The assessment of discomfort/pain will be based on the subject's completion of the 100 mm VAS immediately after treatment.

Subjects will complete the GAIS scale and the 5-point Likert satisfaction scale.

Subjects will be discharged from the clinic and will be instructed to return for the final study visit, Visit 9, Week 20 assessment.

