7.3.4 FINAL STUDY VISIT

Visit 9, Week 20

Subjects will return to the clinic twelve weeks (± 2 weeks) after the last treatment for the final visit. Adverse events and any changes to concomitant medications will be recorded. Photographs will be taken as described above in section 7.3.2. The subject will complete the GAIS scale and the 5-point Likert satisfaction scale. Cutometer® measurements of the treated area will be taken.

The termination form will be completed and subjects will be discharged from the clinic and terminated from the study. The PI will record all reportable events with start dates occurring any time after informed consent is obtained until 7 (for non-serious AEs) or 30 days (for SAEs) after the last day of study participation.

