10.2 STATISTICAL HYPOTHESES

Statistical null hypothesis for primary endpoint: there will be no statistical change in gross elasticity as measured by the Cutometer[®] after treatment with combined RF/PEMF compared to before treatment.

Statistical null hypothesis for secondary endpoint #1: there will be no statistical change in the FWES as rated by blinded clinicians after treatment with combined RF/PEMF compared to before treatment.

Statistical null hypothesis for secondary endpoint #2: there will be no statistical change in the GAIS as rated by the subjects after treatment with combined RF/PEMF compared to before treatment.

Statistical null hypothesis for secondary endpoint #3: there will be no statistical change in the subject satisfaction score after treatment with combined RF/PEMF compared to before treatment.

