10.4 DESCRIPTION OF STATISTICAL METHODS

10.4.1 GENERAL APPROACH

After data set compilation and cleaning, a series of descriptive statistics will first be generated to examine the data set for distributional/potential missing data patterns and sample characteristics. The study team will conduct a series of pooled time series analyses with generalized estimating equations regression (GEE) models.³ These types of non-parametric (i.e., not based on normal distribution assumptions) predictive modeling procedures are capable of using both robust and standard estimating functions to more fully evaluate the influence RF/PEMF treatments and other factors/covariates on serial face gross elasticity measurements. These types of procedures will also enable the study team to examine the potential effects of both *within group* (e.g., face gross elasticity measurements for Patient X at three measurement points) and *between group* (e.g., face gross elasticity measurement changes of younger women versus older women) model variables. A *P*-value of <0.05 will be considered statistically significant.

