10.4.2 ANALYSIS OF THE PRIMARY EFFICACY ENDPOINT(S)

Gross elasticity as measured by the Cutometer® is a ratio expressed as a percentage. Baseline and post-treatment measurements will be taken and analyzed using analysis of variance (ANOVA).

Results will be reported as baseline means with standard deviation, post-treatment means with standard deviation, and individual change for each subject.

Subjects with missing data, non-adherence, or lost to follow-up will not be included in the final analysis dataset.

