10.5 SAMPLE SIZE

The PI has used G*Power 3.10.10 software⁴ to generate *a priori* minimal sample size calculations for the primary study endpoint: changes in *gross elasticity* (GE) repeated measure face measurement in a sample of consented eligible women at three time points: a) prior to RF/PEMF, b) at time of RF/PEMF completion, and c) three months after treatment completion.

These calculations indicate that a minimal sample size of approximately **45** patients would easily afford at least a 0.804784 $1 - \beta$ level of statistical power to detect statistically significant RF/PEMF sample subgroup measurement differences observing a coefficient Alpha of 0.05 two-tailed level of significance. This sample size is based on both a conservative 0.3 (i.e., *Medium*) Effect Size for RF/PEMF treatment and pre-post procedure Cutometer[®] face gross elasticity measurement differences reported in Krueger, et. al (2011).⁵

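### The SAP is finalised only after all open-label data are collected, while the plan leaves open whether the primary test uses two visits or three

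*Combined protocol and SAP*

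**What the plan says.** **Timing.** Section 10.1 reads: "An initial statistical analysis plan has been developed and will be finalized once all data collection is complete". No condition ties finalisation to a point before outcome data are reviewed. Section 10.4.1 has descriptive statistics run on the compiled data set before modelling starts.

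**Test.** Section 10.4.2, on the primary endpoint, states: "Baseline and post-treatment measurements will be taken and analyzed using analysis of variance (ANOVA"). It does not say which post-treatment visits enter. Section 10.4.1 adds: "The study team will conduct a series of pooled time series analyses with generalized estimating equations regression (GEE) models". These models use the same serial elasticity measurements, and the example given has three measurement points. No section says which analysis is primary if the two disagree, and 10.4.9 marks multiplicity as not applicable.

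**Visits.** Section 4.2.1 has gross elasticity (R2) "measured prior to the start of the treatment regimen (baseline), and 20 weeks after completion of the treatment regimen". Section 10.5 describes the primary endpoint as a repeated measure "at three time points: a) prior to RF/PEMF, b) at time of RF/PEMF completion, and c) three months after treatment completion". The null hypothesis in 10.2, "there will be no statistical change in gross elasticity as measured by the Cutometer", compares after with before treatment and names no visit. Section 7.3.3 schedules a week 7 reading ("measurements of the treated area will be obtained"), listed before that day's eighth treatment. For the late reading, 7.3.4 says: "Subjects will return to the clinic twelve weeks (± 2 weeks) after the last treatment for the final visit".

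**Visibility of outcomes.** The study is open-label and single-group (4.1). Cutometer curves are displayed after each measurement (2.1), and the data are saved on the principal investigator's computer (11). No masking of these readings is described.

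**The concern.** The 5% error rate for the primary claim holds only if one test is fixed before its outcome is known. Late finalisation of an SAP does little harm when treatment codes are masked. Here there is no code to mask, and the readings are visible as they are taken. A conflict over the number of visits that stays open until data collection ends can then be settled by someone who has seen which version is significant.

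With no control group, the p-value for change from baseline is the main formal evidence for the primary claim. A reader of the report could not tell a planned test from a selected one, and nothing done afterwards would repair that.

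**Working it through.** **1. The plan's own figure.** Section 10.5 gives power 0.804784 for about 45 patients, effect size 0.3 and two-sided 5%. It names no test, effect-size metric or correlation, so it does not show which test is meant.

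- Paired test, with 0.3 read as the standardised mean change (dz): noncentrality 0.3 × √45 = 2.01 on 44 df, critical t 2.015, power 50.3%.
- One-group repeated-measures ANOVA, with 0.3 read as Cohen's f: noncentrality f² × N × m / (1 − ρ), on (m − 1) and 44(m − 1) df.
  - Two visits, ρ = 0: 0.09 × 45 × 2 = 8.1, power 79.5%. With ρ = 0.5: 16.2, power 97.6%.
  - Three visits, ρ = 0: 0.09 × 45 × 3 = 12.15, power 87.6%. With ρ = 0.5: 24.3, power 99.4%.

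None of these gives 0.804784. A wide search over unstated settings finds a near match for an interaction with five groups, four measurements and correlation 0.15. This study has one group and three Cutometer visits, so that match identifies nothing.

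**2. The two candidate tests.** N = 45, two-sided 5%, no true change.

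- Two visits (4.2.1): t = mean difference / (SD of differences / √45), 44 df. With two visits, a within-subject ANOVA is the same test.
- Three visits (10.5): F = (SS visits / 2) / (SS residual / 88), on 2 and 88 df.

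**3. Error rate if the better result is always taken.** P(either) = P(first) + P(second) − P(both). If the tests were independent this would be 1 − 0.95² = 9.75%. They share data, so the rate is lower. The table comes from simulation with normal data, 200,000 null trials per row and simulation error of about 0.06 points. All correlations are assumed. Unequal patterns are given as baseline–week 7, baseline–Visit 9, week 7–Visit 9.

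| Correlations | Better of paired test and three-visit F | Same, Greenhouse–Geisser F |
|---|---|---|
| all 0.3 | 7.59% | 7.46% |
| all 0.5 | 7.61% | 7.47% |
| all 0.7 | 7.53% | 7.40% |
| all 0.9 | 7.47% | 7.34% |
| 0.8, 0.64, 0.8 | 6.22% | 5.75% |
| 0.5, 0.25, 0.5 | 6.46% | 6.16% |
| 0.9, 0.5, 0.5 | 7.44% | 6.07% |
| 0.5, 0.5, 0.9 | 7.36% | 6.01% |

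The paired Visit 9 test alone rejects in 4.97–5.04% of trials in the equal-correlation rows. At correlation 0.5 the implied overlap is 5.0 + 5.0 − 7.6 = 2.4%. Other runs under equal correlation reached about 7.8%. In the last two rows much of the excess comes from the uncorrected F when correlations are unequal, as the drop to about 6% with the correction shows.

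**4. The GEE models.** Replacing the three-visit F by a small-sample-corrected GEE test over three visits gives 7.5–7.6%. The conclusion does not rely on uncorrected GEE tests.

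**5. Neither test always wins.** At dz = 0.427 the paired test has 80% power at 45. The three-visit F then has about 71% if the change builds in equal steps per visit and about 84% if it plateaus by week 7. Which test looks better depends on the course observed, so a choice made after seeing the data is informative.

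**The case against.** The freedom is narrower than 10.1 alone suggests. Section 10.4.2 is the specific section for the primary endpoint and assigns ANOVA; 10.4.1 is a general approach and can fairly be read as supportive. R2, the single completer data set, the 0.05 level and the two-sided test are all fixed. Read with 4.2.1, the ANOVA becomes a paired test. An initial SAP exists and may already name it. Protocol amendments need IRB approval (13.2), and research data go to a statistician coordinating center (13.4), so those who see individual readings need not be those who settle the SAP.

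Much of this stands, and it limits the size of the problem. It does not close the gap. Section 10.5 applies three time points to the same primary endpoint, no section ranks the analyses, and 10.1 itself says the SAP is not final. Neither IRB approval nor a separate statistician amounts to a lock before review.

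Two stronger readings are tempting. One is that an ordinary ANOVA ignoring the pairing might be used. Section 10.5 speaks of a repeated measure and 10.4.2 reports individual change, so the text points to a within-subject analysis. Adding the unpaired form also leaves the false-positive rate at 5.0%. The other is that week 7 could become the primary visit. That requires setting 4.2.1 aside.

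**Conclusion.** The point holds and should be fixed. Section 10.1 leaves an internal conflict over the primary test, two visits or three, open until outcomes can be seen. If the better result were always taken, the 5% error rate would become about 7.5–7.8% under equal correlations, roughly half as much again, and about 6–7.5% in the unequal patterns examined. These figures assume normal data, 45 completers, no true change and the listed correlations. They are a ceiling for that one choice, not an estimate of what will happen.

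A reader might infer that the team plans to select its test, or that no primary test is named at all. The documents support neither: they show only that selection is possible, and ANOVA is assigned. Finalising an SAP after data collection is not a fault in itself. It matters here because the data are open and no lock before review is stated. If the initial SAP already fixes one test, what remains is to say so and align the sections.

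**What to change.** - **10.1:** state that the SAP will be finalised and dated before any post-baseline Cutometer data are compiled or summarised.
- **10.4.2:** state: *The primary analysis is a two-sided 5% paired (within-subject) test of the change in R2 from baseline to Visit 9; the three-visit repeated-measures ANOVA, the week 7 contrast and the GEE models are secondary or supportive.*
- **10.2:** name Visit 9 in the primary null hypothesis.
- **4.2.1 and 7.3.4:** reconcile the timing of the late visit, given as 20 weeks after completion in one and twelve weeks after the last treatment in the other. There is only one late Cutometer visit, so this is a wording conflict.
- **10.5:** restate the power for the named test, giving the effect-size metric and any correlation assumed.

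The cost is wording, an earlier SAP date and a power recheck, with no extra visits. The team loses freedom to choose a model later, and the stated power may change. If the 0.3 in 10.5 is dz, the paired test has 50.3% power at 45 and 62.8% at the maximum of 60 in 5.4.2, and needs 90 subjects for 80%. If it is Cohen's f over two visits, power at 45 is 79.5% at correlation 0 and 97.6% at 0.5. The plan does not say which is meant.

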10.2 STATISTICAL HYPOTHESES

Statistical null hypothesis for primary endpoint: there will be no statistical change in gross elasticity as measured by the Cutometer[®] after treatment with combined RF/PEMF compared to before treatment.

Statistical null hypothesis for secondary endpoint #1: there will be no statistical change in the FWES as rated by blinded clinicians after treatment with combined RF/PEMF compared to before treatment.

Statistical null hypothesis for secondary endpoint #2: there will be no statistical change in the GAIS as rated by the subjects after treatment with combined RF/PEMF compared to before treatment.

Statistical null hypothesis for secondary endpoint #3: there will be no statistical change in the subject satisfaction score after treatment with combined RF/PEMF compared to before treatment.

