Summary:	This study is an open-label, baseline-controlled, single-center study to measure the change in skin elasticity after combined radio frequency (RF) and pulsed electromagnetic field (PEMF) treatment. Forty-five adult females will undergo weekly treatments over a period of 8 weeks. Skin elasticity will be measured by a Cutometer® prior to beginning treatment, week 7 and 3 months after completion of treatment. Photographs will be taken prior to treatment, at week 4, week 7 and 3 months after completion of treatment. Patient discomfort/pain and satisfaction questionnaires will be completed before, during and after treatment.
Objectives:	The objective is to determine the quantitative change in elasticity of facial skin in subjects who have undergone treatment with combined RF and PEMF.
Endpoint	
Primary endpoint:
 
Quantitatively and objectively measure the change in facial skin elasticity following combined radio frequency and electromagnetic treatment. 
Secondary endpoints:
 
Improvement in facial skin laxity at 7 and 20 weeks post-intervention compared to baseline as assessed by blinded evaluators by photographic assessment utilizing the Fitzpatrick Wrinkle and Elastosis Scale (FWES) scale.Improvement in subject appearance at 7 and 20 weeks post-intervention compared to baseline as assessed by the subject utilizing the Global Aesthetic Improvement Scale (GAIS)Improvement in subject satisfaction with facial skin laxity at 4, 7 and 20 weeks post-intervention compared to baseline as measured by the 5-point Likert Subject Satisfaction questionnaire.
Population:	The study will enroll approximately 45 healthy adult females desiring improvement in facial skin elasticity and tightness.
Phase:	Post-approval
Number of Sites enrolling participants:	One site
Description of Study Agent:	Venus Versa is an FDA approved aesthetic device. The Diamondpolar applicator combining multi-polar RF and PEMF energies will be used in this study. It is approved for non-invasive skin tightening of the face in skin types I - IV.
Study Duration:	8 months

Participant Duration: 5 months

SCHEMATIC OF STUDY DESIGN

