7 STUDY PROCEDURES AND SCHEDULE

7.1 STUDY PROCEDURES/EVALUATIONS

7.1.1 STUDY SPECIFIC PROCEDURES

- Medical history: obtained through interview. History will include age, other medical conditions, and previous invasive or non-invasive cosmetic procedure to the face or neck in the last 6 months.
- Medication history: current medications will be obtained through interview and will include prescription, over the counter, and herbal medications taken 4 weeks prior to study enrollment.
- Physical examination: completed by PI. Focused head and neck skin assessment that will include Fitzpatrick skin type and evidence of scars, infection, or inflammation of the face or neck.
- Imaging assessment: standard photos of the treated area will be taken by the PI using a Nikon D3100 using a 105 mm lens with fixed 2 Nikon flashes using diffuse bounce flash technique that reduces shadows and accentuates the subject's contours.
- Cutometer assessment at baseline, week 7 and at week 20.
- Rater assessment: The FWES will be used to rate the level of skin aging.
- Patient-reported outcomes: subjects will be asked to complete the GAIS questionnaire at weeks 7 and 20, and a 5-point Likert subject satisfaction scale at weeks 4, 7 and 20.

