10.4.3 ANALYSIS OF THE SECONDARY ENDPOINT(S)

Secondary endpoint #1: The FWES is based on an ordinal scale (from 1-9) and will be measured as a single endpoint.

Secondary endpoint #2: The GAIS is a 7-point (-3 to 3) ordinal scale and will be a repeated measure.

Secondary endpoint #3: The subject satisfaction score is a 5-point Likert scale and will be a repeated measure.

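### Null hypothesis #2 is not testable as written: no before-treatment GAIS is collected, the score is itself a rating of change, and Section 10.4.3 names no test or reference value

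*Combined protocol and SAP*

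**What the plan says.** For the GAIS, Section 10.2 sets out what is to be tested as follows: "there will be no statistical change in the GAIS as rated by the subjects after treatment with combined RF/PEMF compared to before treatment".

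The GAIS is collected twice, both times after treatment has begun. Section 7.1.1: "subjects will be asked to complete the GAIS questionnaire at weeks 7 and 20". Section 7.3.3, at Visit 8 (week 7): "Subjects will complete the GAIS scale and the 5-point Likert satisfaction scale". Section 7.3.4, at Visit 9 (week 20): "The subject will complete the GAIS scale and the 5-point Likert satisfaction scale". The schedule of events in 7.3.7 has two marks in the GAIS row, which fits these two visits.

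The endpoint is worded as a judgement of change (synopsis, and again in Section 3): "Improvement in subject appearance at 7 and 20 weeks post-intervention compared to baseline as assessed by the subject utilizing the Global Aesthetic Improvement Scale (GAIS".

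On analysis, Section 10.4.3 has one sentence: "The GAIS is a 7-point (-3 to 3) ordinal scale and will be a repeated measure". The general approach in 10.4.1 adds "The study team will conduct a series of pooled time series analyses with generalized estimating equations regression (GEE) models" and a threshold, a P-"value of <0.05 will be considered statistically significant". Its description and examples concern gross elasticity, and it does not mention the GAIS.

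**The concern.** The hypothesis asks for a difference between a score after treatment and a score before it. The second score is not collected. Scheduling it would not help, because a rating of improvement over baseline has no meaningful value at baseline: each GAIS score is already the change. The same sentence pattern serves all four hypotheses in 10.2. It suits gross elasticity and the FWES, which have baseline readings or photographs, but it does not suit this scale.

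Section 10.4.3 does not supply what is missing. An analyst who follows it literally, with two scores per woman and a repeated-measures model, would naturally report the time effect. That effect answers whether the rating moved between week 7 and week 20, and the endpoint asks whether appearance improved over baseline. A lasting benefit would then look like no change, and a significant result could mean that benefit was fading.

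**Working it through.** The plan gives no power or effect figure for the GAIS, so there is none to reproduce. The power statement in 10.5 concerns gross elasticity and plays no part here.

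**Inputs from the documents.** Scale -3 to 3 (10.4.3); ratings at weeks 7 and 20 (7.1.1, 7.3.3, 7.3.4); N = 45 (10.5); significance level 0.05 (10.4.1).

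**Inputs assumed, because the documents give none.** Latent SD 1 at each visit; correlation r between visits of 0.3, 0.5 or 0.7; several patterns of means; 0 as the no-change value.

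**Step 1: what a time effect estimates.** Let m7 and m20 be the mean GAIS scores at the two visits. A repeated-measures model with a visit term is

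E(score) = b0 + b1 × (1 if week 20, 0 if week 7),

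so b0 = m7 and b1 = m20 − m7. Improvement over baseline lies in m7 = b0 and m20 = b0 + b1. The time effect b1 alone carries no information on it:

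- No effect: m7 = m20 = 0, b1 = 0.
- Lasting benefit: m7 = m20 = 2, b1 = 0.
- Fading benefit: 1.5 to 0.75, b1 = −0.75, with m20 still above 0.
- Growing benefit: 0.5 to 1.25, b1 = +0.75.

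The first two cases are opposite answers to the endpoint's question and give the same b1.

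Week 7 cannot stand in for baseline. In the order of procedures at Visit 8, the GAIS follows seven earlier weekly treatments and that day's treatment.

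**Step 2: approximate size.** For a paired comparison the standardised shift is (m20 − m7) × √45 / √(2(1 − r)). For week 20 against 0 it is m20 × √45 / 1, with √45 = 6.71.

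- Lasting +1: time contrast 0, so the rejection rate is alpha; week 20 against 0 gives 1 × 6.71 = 6.71, far beyond a critical value of about 2.
- Fading 1.5 to 0.75: 0.75 × 6.71 = 5.03 in absolute value. Divided by √1.4 = 1.18 (r = 0.3) this is about 4.3; divided by √0.6 = 0.775 (r = 0.7) it is about 6.5.

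**Step 3: simulation.** 4,000 trials of 45 per scenario and correlation, with bivariate normal values rounded and cut to -3..3. Ranges are over the three correlations.

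| Latent mean, week 7 to week 20 | Week 7 vs week 20 rejects | Week 20 vs 0 rejects |
|---|---|---|
| 0 to 0 | 4.4% to 5.0% | 4.1% to 5.7% |
| 1 to 1 | 5.2% to 5.7% | 100% |
| 2 to 2 | 4.9% to 5.4% | 100% |
| 1.5 to 0.75 | 97.3% to 100% | 99.7% to 99.8% |
| 0.5 to 1.25 | 97.8% to 99.95% | 100% |

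The simulation error on a 5% rate is √(0.05 × 0.95 / 4000) = 0.34 percentage points. A test of the mean of both visits against 0, which is what the intercept of a GEE without a visit term gives, rejected in 100% of runs in every row with benefit and in 4.4% to 5.7% with none.

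The time contrast therefore cannot tell row 1 from row 3. A test against the no-change value separates them completely.

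**The case against.** The strongest reply is that the plan never says it will compare week 7 with week 20. In its context, the repeated-measure sentence may only describe data structure: the FWES is a single endpoint, while the GAIS and satisfaction are collected more than once. A GEE intercept or a one-sample test against 0 fits that sentence just as well. This stands. A reader might infer that the durability contrast is the planned test, but the documents name no test, contrast or model for the GAIS. The figures above therefore describe one natural reading of the text.

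A second reply is that the wording is merely loose: since the synopsis and Section 3 place the comparison with baseline inside the rating, hypothesis #2 can be read as saying that women report no change. That is probably what was meant. It is not what 10.2 says, and the intended version still needs a reference value that no section supplies.

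Third, the documents print no anchors for the scale. That 0 means no change follows reasonably from its name and symmetric range, but it is an inference.

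Fourth, the roughly 5% result is true by construction, since two equal distributions are being compared. That is correct; it also means the result does not depend on the assumed SD or correlation. The 97% to 100% figures do depend on them. A reader might further infer that fading benefit would be reported as efficacy. The documents do not show this: individual data are to be listed by time point (10.4.10), and the direction of change would be visible.

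The synopsis line about questionnaires before, during and after treatment does not rescue the hypothesis, because it concerns discomfort/pain and satisfaction.

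**Conclusion.** The point holds in this form. Null hypothesis #2 cannot be tested as written, because its before-treatment term is not collected and would have no meaning for a rating of change. Section 10.4.3 leaves the test and the reference value open. If the usual time effect is chosen, equal lasting improvement leads to rejection in only about 5% of trials whatever its size, while a test against 0 rejected in every simulated trial at latent means of +1 and +2 with N = 45. The first figure needs only equal distributions at the two visits. The second rests on the assumed SD of 1 and on 0 being the no-change value.

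The practical weight is moderate. The GAIS is a secondary endpoint in an open-label study, and Section 4.2.2 gives the secondary endpoints a supporting role. It should still be settled early: Section 10.1 finalises the analysis plan only after data collection ends, so the choice between two analyses that can reach opposite conclusions would be made when the data already exist.

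**What to change.** 1. **Section 10.2.** Restate hypothesis #2: the GAIS score at week 20 is centred on the scale's no-change value, and likewise at week 7. Say which visit carries the hypothesis or how the two results are read together, since the synopsis lists both equally.
2. **Section 10.4.3.** Print the seven anchors and confirm that 0 is the no-change category. Name the test: a one-sample Wilcoxon signed-rank test against 0 at each visit, with the handling of zero scores stated, because a zero is a valid answer here. An equivalent choice is a GEE intercept tested against 0; any covariates should then be centred so that the intercept remains the mean score.
3. **Same section.** Label any week 20 versus week 7 contrast as durability only.
4. **Optional.** Report the proportion scoring at least +1 as a descriptive summary.

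The cost is a few sentences in two sections, with no new data, visits or subjects. The change should be made before the ratings are analysed.
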